### Protocol deviations

As per ICH E3 guideline, a protocol deviation is any change, divergence, or departure from the study design or procedures defined in the protocol, with or without impact to the patient safety or the efficacy assessments. Protocol deviations are displayed in the Clinical Study Report (CSR) as a metric of the feasibility and reliability of the study. The list of protocol deviations are presented in the table below and can be updated if necessary before breaking the blind. Protocol deviations will be gathered from monitoring files, clinical database and external vendors of off-site data (Laboratory data, ECG...)

Protocol deviations will be split in major and non major deviations. A major deviation is defined as a deviation being an impact on the primary criteria. A first categorisation is done in this document, then categorisation will be done before breaking the blind during the statistical data review meeting. The decision will be duly described in the meeting minutes.

The deviations are listed in the table below:

Category	Description	Source	Status
Inclusion criteria not met	Adult healthy volunteers not aged at least 18 years old	Clinical database (prior amendment 2)	Non major
	Adult healthy volunteers not aged at least 18 years old and below 60 (exclusive)	Clinical database (after amendment 2)	Non major
	Subject not having read the information and not provided his/her consent to participate in writing by dating and signing the informed consent prior to any trial-related procedure being conducted	Monitoring	Major
	Subject not assessed as healthy by a comprehensive clinical assessment (detailed medical history and complete physical examination)	Clinical database	Non major
	Subject without a Body Mass Index (BMI) > 19 kg/m  and < 28 kg/m  or a weight at least of 40 kg for female and 50 kg for male and at maximum of 100 kg	Clinical database	Non major

CONFIDENTIAL	STATISTICAL ANALYSIS PLAN N° GDX-44-006  VERSION N° 2.0      DATED: 24JUL2018  	  Page 18 / 57
--------------	--	---

	Subject not able or not willing to participate in the trial	Clinical database	Non major
Non-Inclusion criteria met	Subject with any history or family history of inherited or acquired Long QT syndrome (LQTS)	Clinical database	Major
	Subject with any history or family history of risk factors for Torsade de Pointe (TdP), unexplained loss of consciousness or convulsion	Clinical database	Major
	Subject with any history of clinically significant bradycardia	Clinical database	Major
	Subject with any history of clinically significant cardiac impairment by decreasing of left ventricular ejection fraction (LVEF)	Clinical database	Major
	Subject with any history of clinically significant arrhythmia (including Wolf-Parkinson-White syndrome)	Clinical database	Major
	Subject with presence of cardiac pacemaker	Clinical database	Major
	Subject with frequent headaches and/or migraine, recurrent nausea and/or vomiting (more than twice a month)	Clinical database	Non major
	Subject with abnormal 12-lead ECG: PR < 120 ms or PR > 200 ms, QRS > 100 ms, QTc > 450 ms, flat T-waves at screening visit (results provided by the independent ECGs Core Laboratory)	Clinical database	Major
	Subject with following abnormal vital signs after 10 minutes resting in supine position at screening visit: <90 SBP >160mmHg, <45 DBP >90mmHg, <50 HR >80bpm	Clinical database (prior amendment 2)	Non major
	Subject with following abnormal vital signs after 10 minutes resting in supine position at screening visit: <90 SBP >160mmHg, <45 DBP >90mmHg, <45 HR >80bpm	Clinical database (after amendment 2)	Non major
	Subject with any history or presence of relevant cardiovascular, pulmonary, gastrointestinal, hepatic, renal, metabolic, hematological, psychiatric, systemic, ocular, or infectious disease; any acute infection or signs of acute illness	Clinical database	Non major
	At Day-1: K+ < 3.6 mmol/L, Mg++ < 0.8 mmol/L, eCCr < 90 mL/min, impaired liver f./ALT-AST > 2xULN	Clinical database / Monitoring (prior amendment 2)	Non major

CONFIDENTIAL	STATISTICAL ANALYSIS PLAN N° GDX-44-006  VERSION N° 2.0      DATED: 24JUL2018  	  Page 19 / 57
--------------	--	---

	At Day-1: K+ < 3.5 mmol/L, Mg++ < 0.66 mmol/L, eCCr < 90 mL/min, impaired liver f./ALT-AST > 2xULN	Clinical database (after amendment 2)	Non major
	Subject carrier of: HBs antigen, anti-HCV antibodies, anti-HIV1 antibodies, anti-HIV2 antibodies at screening	Clinical database	Non major
	Subject with any history of severe allergic or anaphylactic reactions to any allergen including drugs and contrast agents, or allergic disease diagnosed and treated by a physician	Clinical database	Non major
	Subject with any history of tendinopathy following a fluoroquinolone treatment	Clinical database	Non major
	Subject with any history of allergy to moxifloxacin or one of its compounds or other moxifloxacin contra-indications according to the SmPC description	Clinical database	Non major
	Subject with known contra-indication(s) to the use or with known sensitivity to one of the products under investigation or to drugs from a similar pharmaceutical class	Clinical database	Non major
	Subject treated with any concomitant medications which could induce a QT prolongation	Clinical database	Major
	Subject with presence of narcotics or alcohol abuse (alcohol consumption > 40 grams/Day) at screening	Clinical database	Non major
	Subject smoking more than 10 cigarettes or equivalent /Day, unable to stop smoking during the confinement period	Clinical database	Non major
	Subject having an excessive consumption of beverages with xanthine bases (tea, coffee, chocolate) (>6 cups or glasses /Day) and not able to refrain from consuming grapefruit (fresh fruit, juice, ice...) the day before inclusion and during the confinement period	Clinical database	Non major
	Subject having done a blood donation within 3 months before first trial product administration	Clinical database	Non major
	Subject having received any medication within 21 days prior to inclusion, or within 5 times the elimination half-life of that drug, whichever the longest, with the exception of hormonal contraception for	Clinical database	Non major

CONFIDENTIAL	STATISTICAL ANALYSIS PLAN N° GDX-44-006  VERSION N° 2.0      DATED: 24JUL2018  	  Page 20 / 57
--------------	--	---

	female and of Hormonal Replacement Therapy (HRT) in case of menopausal volunteers and paracetamol		
	Subject having received an administration of any contrast agent within 2 weeks before inclusion, or scheduled to receive any contrast agent within 3 months after the last IMP administration	Clinical database	Non major
	Subject having participated to a clinical trial involving an investigational drug or device within 21 days prior to screening, or within 5 times the elimination half-life of that drug whichever the longest	Clinical database	Non major
	Subject having a planned simultaneous participation to another clinical trial involving an investigational drug or device	Clinical database	Non major
	Subject having an inability or unwillingness to cooperate with the requirements of this trial	Clinical database	Non major
	Subject having a planned interventions (surgery, radiotherapy, chemotherapy or others) during the course of the trial	Clinical database	Non major
	Subject with any condition which, based on the investigator's clinical judgment, would prevent the subject from participating in all trial assessments and visits (for example: mental or physical incapacity, language comprehension, geographical localization, etc.)	Clinical database	Non major
	Pregnant or breast-feeding (a childbearing potential woman or amenorrhea less than 12 months must have a negative pregnancy test at inclusion and be using a medically approved contraception method)	Clinical database / Monitoring	Non major
Subject not withdrawal as per protocol	Stopping rules detected on laboratory measurements and subject not withdrawn: increase in serum creatinine by more than 25% or 0.5 mg/dL (44 umol/L) compared to the baseline value	Laboratory database	Non major
	Stopping rules detected on ECG measurements and subject not withdrawn: QTc Friderica > 500 ms or an increase of > 60 ms over the baseline	ECG database	Non major

CONFIDENTIAL	STATISTICAL ANALYSIS PLAN N° GDX-44-006  VERSION N° 2.0      DATED: 24JUL2018  ██████████	██████████  Page 21 / 57
--------------	---	--------------------------------

	Stopping rules detected on ECG measurements and subject not withdrawn: Torsade de pointes event / Ventricular tachycardia / Ventricular fibrillation flutter / Seizures	ECG database	Non major
	Subject received a contrast agent within two weeks before the inclusion up to the end of confinement period and subject not withdrawn	Clinical database	Major
	Any exam performed after a withdrawal of consent	Clinical database, Laboratory database, ECG database	Non major
Unblinding	The blind was not maintained on-site	Monitoring	Non major
	The blind was not maintained off-site	Monitoring	Major
	The code was broken	Clinical database	Major
Forbidden concomitant medication	Concomitant medication taken during the confinement period having an impact on the primary criteria	Monitoring	Major
Trial product deviation	Subject randomisation not followed the sequential list of sequences	Clinical database	Non major
	IMP/AMP administered is not the IMP/AMP allocated by randomisation	Randomisation database	Major
	The volume actually administered is different from 10% to 20% than the calculated one	Clinical database	Non major
	The volume actually administered is different of more than 20% than the calculated one	Clinical database	Major
	Power injector not used	Clinical database	Non major
	The actual injection rate is different than 2mL/s	Clinical database	Non major
	Saline flush volume administered not at minimum of 10 mL	Clinical database	Non major
	Location of injection site is not adequate	Clinical database	Non major
	The dose of AMP actually administered is different from 400 mg	Clinical database	Non major
	Temperature excursion for trial product	Monitoring	Non major
	Extravasation	Clinical database	Major

CONFIDENTIAL	
STATISTICAL ANALYSIS PLAN N° GDX-44-006
 
VERSION N° 2.0      DATED: 24JUL2018
 
██████████
	
██████████
 
Page 22 / 57

--------------	--	---------------------------------------

Missing data	Age is missing	Clinical database	Non major
	Sex is missing	Clinical database	Non major
	Weight is missing at screening visit	Clinical database	Non major
	Height is missing	Clinical database	Non major
	Race is missing	Clinical database	Non major
	Physical examination not performed	Clinical database	Non major
	Vital signs not measured	Clinical database	Non major
	Other contrast agent administration not completed	Clinical database	Non major
	Urine sample not done or missing at screening visit	Clinical database	Non major
	Pregnancy test is missing	Clinical database	Non major
	12-lead safety ECG not performed in triplicates	Clinical database	Non major
	12-lead safety ECG results missing	ECG database	Non major
	12-lead safety ECG from paper instead of digital analysis	ECG database	Non major
	12-lead Holter ECG not performed	Clinical database	Major
	12-lead extracted QTCF from Holter ECG with more than 3 measurements of triplicates at baseline missing	ECG database	Major
	12-lead extracted Holter ECG not performed in triplicates	ECG database	Non major
	Blood sample for central laboratory assessment not performed	Clinical database	Non major
	Laboratory biochemistry results missing	Laboratory database	Non major
	Laboratory hematology results missing	Laboratory database	Non major
	Urine sample for long term elimination not performed	Clinical database	Non major
	Urinary result for long term elimination missing	PK database	Non major
	Blood sample for long term elimination not performed	Clinical database	Non major

CONFIDENTIAL	
STATISTICAL ANALYSIS PLAN N° GDX-44-006
 
VERSION N° 2.0      DATED: 24JUL2018
 
██████████
	
██████████
 
Page 23 / 57

--------------	--	---

	Blood sample results for long term elimination missing	PK database	Non major
	Blood sample for plasma concentration not performed	Clinical database	Non major
	Results for plasma concentration missing	PK database	Non major
	Tolerance at injection site not performed	Clinical database	Non major
	VAS questionnaire not completed while subject reported pain	Clinical database	Non major
	Visit not done	Clinical database	Non major
Non respect of study's schedule and procedures	Urine sample for drug screening not performed at latest the day before first administration	Clinical database	Non major
	Blood samples collection for P03277 plasma concentration assessment not performed after vital signs	Clinical database	Non major
	Blood samples collection for laboratory data not performed before IMP /AMP administration of first period	Clinical database	Non major
	Vitals signs not performed at scheduled time	Clinical database	Non major
	Blood samples collection for P03277 plasma concentration not performed at scheduled timepoint	Clinical database	Non major
	12-lead Holter ECG not performed at scheduled time	ECG database	Non major
	12-lead safety ECG not performed at scheduled time	ECG database	Non major
	Initiation of Holter not performed 1 hour before administration	Clinical database	Non major
	12-lead Holter ECG not performed according to procedures	Monitoring	Non major
	12-lead safety ECG not performed according to procedures	Monitoring	Non major
	Blood sample collection not performed at scheduled time	Clinical database	Non major
	Not allowed retest	Monitoring	Non major
	VAS questionnaire not correctly printed	Monitoring	Non major

Subjects presenting at least one major protocol deviation will be excluded from the Per Protocol Set.

CONFIDENTIAL	STATISTICAL ANALYSIS PLAN N° GDX-44-006  VERSION N° 2.0      DATED: 24JUL2018  	  Page 24 / 57
--------------	--	---

Frequency and percentages of subjects with protocol deviations will be presented by sequence group and overall breaking down by status (major/non major). A listing of all protocol deviations will also be provided in CSR appendix 16.2.2 and major protocol deviations will be flagged.

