5.3.4 Individual Trial Treatment Unblinding

The blinding system will be made of two sets of envelopes.

One sealed envelopes set is kept at the phase I clinical trial unit, the other at the Guerbet pharmacovigilance Representatives (Sérénité 24/24h).

The sets of envelopes should be kept in a safe place and accessible to any person authorised to unblind.

In case of an adverse event occurring for a subject and which nature would require immediate knowledge of the allocated IMP, the individual trial treatment may be unblinded, if absolutely necessary for the safety of the subjects and if unblinding impacts the management of medical care ([see section 9.5](#)).

Conditions and procedure for breaking the code will be reviewed with the investigator and his/her team during the initiation visit.

The persons authorized to unblind trial product during the trial usually are: the principal investigator and the Sponsor Pharmacovigilance physician/officer.

If a Guerbet representative receives an external request for unblinding (Authorities, health care professionals taking care of the subject, etc.), he/she must inform the Sponsor Pharmacovigilance Physician/Officer.

If the investigator and the Sponsor Pharmacovigilance physician/officer unblind the trial product, he/she must inform the Clinical Project Manager as soon as possible by letter, fax or e-mail but shall not reveal the nature of the trial product in order to protect as much as possible the double-blind design of the trial.

Unblinding must be documented on the opened envelope by indicating the subject's identification number, age and gender, the date, time and the reason for unblinding, the identity of the person who performed the unblinding.

Please refer to [section 9.5](#) for detailed information on subject safety monitoring.

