8.3.3.5 Blinded Assessment of ECGs

ECGs from Holter recorder database including all evaluable ECGs will be assessed by one or more expert reader(s), with expertise in the interpretation of ECGs for QT and arrhythmia assessment, who will not participate in the trial, and does not have affiliation with the institution where the trial will be conducted. The reading will be performed in a strictly fully blinded manner.

ECGs Core laboratory has to ensure that all ECGs (except safety ECGs) of a given patient have to be read on the same day by the same reader and the reader has to be blind about subject, product, date and time-point identifier [2]

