### 5.2. Data sets analysed and protocol deviations

#### Data sets analysed

There will be four subject sets defined for this study: All enrolled subjects set, the Safety Set (SS), the Full Analysis Set (FAS) and the Per-Protocol Set (PPS).

All enrolled Subjects Set will include all subjects who signed their informed consent form. This set will be used for subject disposition summaries and individual listings.

All subjects who failed the screening visit (not selected) or withdrawn from the study before the randomization are screen-failed subjects and will be presented in the all enrolled data set. Those subjects have different data collected depending on the selection status i.e. complete screening visit and inclusion visit data collected for volunteers who have been selected at screening visit while only screening visit data were collected for subjects who did not comply with the eligibility criteria.

The Safety Set will include all subjects receiving at least one administration of IMP, regardless of the quantity. This set will be used for evaluation of safety and description of demographic data and baseline characteristics.

The Full Analysis Set will include all randomized subjects. This set will be used for evaluation of cardiac safety and description of demographic data and baseline characteristics.

The Per Protocol Set will be a subset of the FAS and will include all subjects who have no major protocol deviations throughout their whole trial period. Major deviations will be defined as having an impact on the primary criterion. Primary analysis will be performed on this set.

The number of subjects by analysis set will be tabulated by sequence group and overall.

The following table describes how the above defined subjects sets will be used in the different analyses conducted.

CONFIDENTIAL	STATISTICAL ANALYSIS PLAN N° GDX-44-006  VERSION N° 2.0      DATED: 24JUL2018  	  Page 17 / 57
--------------	--	---

Analyses Sets	Safety Set	Full Analysis Set (FAS)	Per protocol (PP) Set
Demographic data and baseline characteristics	✓	✓	✓ *
Exposure	✓		
Cardiac safety assessment		✓	✓
Safety assessment	✓		

\*: If the difference between FAS and PP set is greater than 10%

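### Classing every code break as a major deviation removes whole subjects from the primary set for a reason usually tied to an adverse event, although the ECG reader stays blind

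*SAP*

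**What the plan says.** The Unblinding block of the deviation table in SAP 5.2 has three rows:

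- "The blind was not maintained on-site": Non major.
- "The blind was not maintained off-site": Major.
- "The code was broken": Major, with the clinical database as source.

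The same section gives the consequence: "Subjects presenting at least one major protocol deviation will be excluded from the Per Protocol Set". Exclusion is by subject, since the set requires "no major protocol deviations throughout their whole trial period". The standard for the label is also stated: "Major deviations will be defined as having an impact on the primary criterion".

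SAP 5.5.1.2 runs the primary analysis on the Per Protocol Set, and 5.5.2 repeats it on the Full Analysis Set. SAP 5.5.4.3 runs the concentration-QTc analysis on the Per Protocol Set, with its own 10 ms decision rule and no stated repeat on the Full Analysis Set.

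Protocol 5.3.4 says that, for an adverse event whose nature demands knowing the product, "the individual trial treatment may be unblinded, if absolutely necessary for the safety of the subjects", provided this also affects medical care. On the Holter ECGs, Protocol 8.3.3.5 says "the reader has to be blind about subject, product, date and time-point identifier".

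**The concern.** A major deviation should be one that can affect the QTcF measurement. A code break made to look after a subject informs the investigator or the sponsor's pharmacovigilance staff. The primary endpoint is read elsewhere, by someone who does not know even whose ECG it is.

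The exclusion is therefore not justified by the quality of the data, yet its usual trigger is something that happened to the subject after dosing. In a non-inferiority safety analysis that is a poor reason to lose a subject. If the event was a cardiac reaction to P03277, the lost data are the data the trial exists to collect, and the estimate falls.

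The concentration-QTc analysis has the same exposure without a stated Full Analysis Set repeat behind it.

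**Working it through.** **Does a code break meet the SAP's definition of major?**

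1. The primary criterion is QTcF change from baseline, taken from Holter ECGs (SAP 2.2 and 2.2.1).
2. Those ECGs are read off-site by experts who take no part in the trial and have no affiliation with the site (Protocol 8.3.3.5).
3. The break is contained. Whoever unblinds must not pass on the nature of the product when informing the project manager (Protocol 5.3.4). SUSAR unblinding stays hidden from the investigator and from staff who manage and analyse the trial (Protocol 9.5).
4. Loss of blind off-site already has its own Major row.

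No documented route leads from a code break to the QTcF reading. By the SAP's own test the row should not be Major unless the reader was informed.

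**Who would be lost because of this row?** Protocol 10.2 discontinues a subject for ventricular tachycardia, seizure, or QTcF above 500 ms or up by more than 60 ms. After such an event in periods 1 to 3, later Holters are not done, and an unperformed Holter is itself Major. Such a subject would leave the Per Protocol Set anyway. The row has its own effect in three situations: an event in period 4 after which the Holter is completed; an event during follow-up, when related events and events of special interest are still collected; and an event that is not a listed stopping rule (syncope, for example) after which the subject continues.

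**The plan's sample size.** Inputs from SAP 3.3: σ = 9 ms, δ = 2 ms, margin 10 ms, one-sided α = 0.05, power 85%, L = 9.

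- Formula: N = 2 × [t_α(N−2) + t_β′(N−2)]² × [σ/(δ−10)]², with β′ = 1 − 0.85^(1/L).
- L = 9: β′ = 0.0179, N = 37.9, rounded up to 38. The stated 40 is reproduced within two subjects.
- L = 11 (the timepoints actually tested, SAP section 4): N = 39.5, rounded up to 40.

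**Power if subjects are lost** (per dose, L = 11, same formula; the number lost is assumed):

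| Analysed N | Power |
|---|---|
| 48 | 94.5% |
| 47 | 93.8% |
| 44 | 91.1% |
| 40 | 85.8% |
| 39 | 84.1% |
| 36 | 77.8% |

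The lower rows apply if recruitment stops at 40 evaluable subjects. Evaluable is defined by completing the last Holter, so a code-broken subject counts towards the 40 but is not analysed.

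**Shift in the mean.** Suppose 47 subjects average 2 ms and one has effect E on P03277. Dropping that one lowers the mean by (E − 2)/48.

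- E = 30 ms: 28/48 = 0.58 ms.
- E = 60 ms: 58/48 = 1.21 ms.
- Two such subjects, by 2(E − 2)/48: 1.17 to 2.42 ms.

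For comparison, the half-width of the 90% interval at N = 48 is t(0.95, 46) × 9 × √(2/48) = 3.08 ms, and the assumed effect lies 10 − 2 = 8 ms below the margin.

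**The case against.** The strongest reply is that the safeguards are already there. The Full Analysis Set holds all randomised subjects, the primary test is repeated on it, and the outlier counts for QTcF default to it, so a discrepancy would be visible. The table is a first categorisation, settled at a blinded and minuted data review meeting. Both points stand and limit the damage. They do not remove the defect: the repeat is supportive, no rule covers disagreement between the sets, and a case-by-case decision is weaker than a stated rule.

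It can also be said that the rows describe different things. A formal break reveals the subject's sequence and may be made off-site by pharmacovigilance. That is fair. The rows fit badly together, but they do not flatly contradict each other, and the real gap is that the code-break row does not say who learned the code.

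A reader might infer that subjects with serious reactions are dropped as a class. The documents do not support this. A serious event is not on the deviation list, only a broken code is. The trigger need not be serious, and Protocol 5.3.4 also mentions outside requests for unblinding, including from authorities.

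A reader might also infer that the rule necessarily favours a negative trial. That is not established. Moxifloxacin is open label, so a break normally concerns P03277 or placebo. If the reaction followed placebo and raised QTcF, dropping the subject would raise the drug-placebo difference. A non-cardiac event need not move QTcF at all. Nothing ties a follow-up event to the subject's earlier QTcF, so a loss at that stage is first of all a loss of valid data.

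**Conclusion.** The concern holds as a matter of rule, not of demonstrated bias. The code-break row fails the SAP's own criterion for a major deviation and lets an event after dosing remove a whole subject, possibly with four complete Holters, from two analyses that each have a 10 ms decision rule.

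The size is probably small. Breaks are tightly restricted, no rate is given, and zero is plausible. One dropped subject with an assumed 30 to 60 ms effect on P03277 moves the mean by about 0.6 to 1.2 ms at N = 48, well inside the 3.1 ms half-width. That range rests on the assumed individual effect, on the remaining subjects averaging the planned 2 ms, and on the event following P03277. Power stays above 91% with up to four losses from 48. It is more sensitive if recruitment stops at 40.

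The change is worth making because it costs almost nothing and removes an avoidable outcome-related exclusion.

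**What to change.** Before unblinding, in the deviation table of SAP 5.2:

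- Make the code-break row Non major when the ECG core-lab reader was not informed.
- Keep the off-site row Major, and word it so that it means loss of blind reaching the reader.
- State that pharmacovigilance unblinding of a SUSAR (Protocol 9.5) does not by itself exclude the subject.

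Code-broken subjects will still appear in the deviation listing already planned for CSR appendix 16.2.2.

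The cost is a short edit to one block of the table. The downside is that a few subjects whose site staff knew the code stay in the Per Protocol Set, which the SAP already accepts for on-site loss of blind. The rules on when a code may be broken are untouched.

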10.2 Reasons for Subject's premature discontinuation

Screening Failure: a subject may be discontinued from trial in case of non-fulfillment of eligibility criteria. Subject having been screened and meeting all selection criteria but not included in the 28 days screening period could be re-screened. This implies that the subject will sign a new informed consent form before performing the screening visit and will be allocated with a new trial subject number.

Criteria for premature discontinuation of subjects:

- Adverse Event (according to the investigator's judgement);
- Withdrawal of subject's consent;
- Subject lost to follow-up (date of last contact will be documented in the medical file and the eCRF). Any effort will be undertaken to know the reason for this loss to follow-up and/or to exclude any adverse reaction as this reason. This will be documented in the medical file;
- Discovery of an unexpected, significant, or unacceptable risk to the subjects enrolled in the trial;
- At the discretion of the investigator if the subject safety or well-being is not compatible with trial continuation;

Specific subjects stopping rules:

If any of the events described below occurs, injection of IMP/AMP should not be done and the subject should be discontinued from the trial:

- Torsade de pointes event;
- Ventricular tachycardia;
- Ventricular fibrillation and flutter;
- Seizures;
- QTc Fridericia >500 ms or an increase of > 60 ms (ECG Core laboratory data) over the baseline (the baseline for safety ECG is defined as the 12-leads triplicate ECGs recorded within 1 hour prior to each administration) measurement before each IMP/AMP administration;
- Renal toxicity characterized by an increase in serum creatinine by more than 25% or 0.5 mg/dl (44 µmol/l) compared to the baseline value;
- Any events which investigator or Guerbet considers raising a significant concern.

Specific trial stopping rules:

If this event described below occurs, enrolment should be suspended and the trial will be on hold:

- Torsade de pointes event in 1 subject;
- Sudden death in 1 subject;
- Ventricular tachycardia in 2 subjects;
- Ventricular fibrillation and flutter in 2 subjects;
- Seizures in 2 subjects;
- QTc Fridericia >500 ms or an increase of > 60 ms (ECG Core laboratory data) over the baseline (the baseline for safety ECG is defined as the 12-leads triplicate ECGs recorded within 1 hour prior to each administration) repeated in 2 subjects;

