#### Test

Differences between means will be tested through the model for each timepoint and for the two doses of P03277 using Student's t-test.

For each timepoint, the two-sided 90% confidence intervals of the difference between each of the two doses of P03277 and placebo is calculated for testing the hypotheses.

The trial will be considered as successful if no test is significant that is to say if the upper range of the 90% CI is lower than 10 ms for all tests.

The appropriateness of a linear model will be assured by inspecting the goodness of fit by looking at normal QQ plots for the residuals and plots of the residuals over predicted values.

The primary analysis will be performed using the Per Protocol Set.

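### A subject stopped for QTcF prolongation in periods 1 to 3 can, on a literal reading of SAP 5.2, lose all completed periods from the primary analysis

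*SAP*

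**What the plan says.** Four rules combine.

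- **Primary set.** SAP 5.5.1.2: "The primary analysis will be performed using the Per Protocol Set". Protocol 11.3.2 and 11.4.6 and SAP 3.9 agree. The concentration-QTc analysis in SAP 5.5.4.3, which has its own 10 ms decision rule, also uses the Per Protocol Set.
- **Unit of exclusion.** The set "will include all subjects who have no major protocol deviations throughout their whole trial period" (SAP 5.2). The subject is therefore removed as a whole: "Subjects presenting at least one major protocol deviation will be excluded from the Per Protocol Set".
- **Missing Holter.** In the Missing data block of the SAP 5.2 deviation table, the row "12-lead Holter ECG not performed" has status Major. No exception is given for subjects who have left the trial.
- **Stopping rule.** Protocol 10.2 lists "QTc Fridericia >500 ms or an increase of > 60 ms (ECG Core laboratory data) over the baseline" among the events after which "injection of IMP/AMP should not be done and the subject should be discontinued from the trial".

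The same table has a row for a stopping rule met on ECG with "subject not withdrawn: QTc Friderica > 500 ms or an increase of > 60 ms over the baseline". Its status is Non major.

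Three provisions soften the effect. SAP 5.5.2 repeats the primary analysis on the Full Analysis Set (FAS), meaning all randomized subjects. SAP 5.5.4.2 counts QTc values and increases above fixed thresholds on the FAS. SAP 5.2 calls its table a first categorisation, to be completed at a data review meeting before the blind is broken.

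**The concern.** Taken literally, the rules make membership of the primary analysis set depend on the outcome being tested. A subject whose QTcF passes the stopping threshold in period 1, 2 or 3 is discontinued as the protocol requires and so has no Holter in the remaining periods. That is a major deviation by the table, and the completed periods go too, including the one with the prolongation.

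The table also treats the two possible courses the wrong way round. Following the protocol can remove the subject, while failing to withdraw the same subject leaves the data in.

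At stake is the P03277-minus-placebo difference that is compared with 10 ms. The concentration-QTc decision rule rests on the same set and can lose the same subject. The FAS repeat keeps the data, but neither document says what follows if it disagrees with the Per Protocol result.

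**Working it through.** **1. Reproduce the plan's figure.** Inputs from Protocol 11.2 and SAP 3.3: σ = 9 ms, δ = 2 ms, margin 10 ms, one-sided α = 5%, power 85%, L = 9.

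- β′ = 1 − 0.85^(1/9) = 0.0179.
- At N = 38 (36 df): N = 2 × (1.688 + 2.181)² × (9/8)² = 37.9, so 38 against the stated 40.
- With the 11 timepoints that the SAP tests, the formula gives 39.5, so 40.

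The stated figure is reproduced closely enough to use its inputs.

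**2. Follow a stopped subject through the rules.**

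| Course of events | Row in SAP 5.2 | Status | In the Per Protocol Set? |
|---|---|---|---|
| Meets QTcF rule in period 1, 2 or 3; withdrawn | Holter not performed (later periods) | Major, read literally | No; completed periods lost |
| Meets QTcF rule; not withdrawn | Stopping rule met, not withdrawn | Non major | Yes |
| Meets QTcF rule in period 4 | No later Holter to miss | None from this row | Yes |

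**3. Direction.** The stopping rule applies to every product.

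- Event after P03277: removing the subject lowers the P03277-minus-placebo difference and favours passing.
- Event after placebo: removal raises the difference and works against passing.
- Event after moxifloxacin: no fixed direction for P03277.

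**4. Shift in the mean (illustration).** Assumptions: the stopped subject's placebo-corrected Holter change is +60 ms at one timepoint, the others average 2 ms, and both the P03277 and placebo periods were completed.

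- N = 40: mean with the subject = (39 × 2 + 60)/40 = 3.45 ms; without, 2 ms. Shift = (60 − 2)/40 = 1.45 ms.
- N = 48: shift = (60 − 2)/48 = 1.21 ms.

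The room between expected effect and margin is 10 − 2 = 8 ms, so these shifts are 18% and 15% of it.

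**5. Would one such subject change the conclusion?** Simple paired calculation at N = 40, with variance of a difference 2 × 9² = 162 in the other 39 subjects.

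- Kept: SD = √[(38 × 162 + 39 × 1.45² + 56.55²)/39] = 15.55; SE = 15.55/√40 = 2.46; upper 90% limit = 3.45 + 1.685 × 2.46 = 7.6 ms.
- Dropped: SE = √(162/39) = 2.04; upper limit = 2 + 1.686 × 2.04 = 5.4 ms.

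Both are below 10 ms. If the others average 5 ms, the same steps give 10.4 ms kept and 8.4 ms dropped, so the conclusion changes. At N = 48 and 5 ms they give 9.8 and 8.1 ms, and it does not.

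**6. Simulation of the crossover mixed model.** N = 40, 150 runs per scenario, one timepoint, baseline and sex omitted. Assumed: between-subject SD 5 ms and +65 ms on the high dose in each stopped subject. The table gives the share of runs in which dropping the stopped subjects moves the upper limit from at or above 10 ms to below it. Ranges cover stopping before and after the placebo period.

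| True effect in the others | One stopped subject | Two stopped subjects |
|---|---|---|
| 2 ms | 5–8% | 20–33% |
| 5 ms | 24–35% | 47–59% |

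Under Protocol 10.2 the trial goes on hold once two subjects meet the QTcF rule.

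**The case against.** The strongest reply is that the Major row need not apply. SAP 5.2 says "a protocol deviation is any change, divergence, or departure from the study design or procedures defined in the protocol", and a subject withdrawn under Protocol 10.2 has departed from nothing. The sample-size sections handle such subjects as dropouts, and the table's row for a visit that did not take place is Non major. This reading is reasonable and may be what was intended. It is not written down, and the Holter row carries no exception.

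Next, the table is provisional and the blinded meeting can reclassify. That stands, but nothing directs the meeting to do so. A rise above 60 ms is visible without the treatment code, so the choice is better fixed beforehand.

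A reader might infer more than the documents support:

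- *That the prolongation disappears from the report.* It does not. The FAS repeat and FAS outlier counts retain it, and major deviations are listed and flagged.
- *That the exclusion always helps the product.* It does so only when the event follows P03277 in periods 1 to 3.
- *That a 60 ms stopping threshold equals a 60 ms effect on the endpoint.* The rule uses safety ECGs against one pre-dose triplicate, without placebo correction. The endpoint uses Holter extractions, a baseline averaged over three triplicates, and placebo correction. The +60 ms input is an assumption.
- *That the trial loses needed precision.* Eight subjects beyond the 40 required are randomized to cover losses. The issue is selection.
- *That deviations confined to one period, such as extravasation or a wrong volume or product, must also be handled by period.* Whole-subject exclusion follows Protocol 11.3.2 and is a defensible convention, and no selection toward passing is shown for those events.

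**Conclusion.** The concern holds on the literal text. SAP 5.2 allows an outcome-dependent exclusion from the primary analysis for a subject stopped for QTcF prolongation in periods 1 to 3, and it treats a subject wrongly kept on more leniently than one correctly withdrawn. The bias favours a negative QT finding when the event follows P03277.

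The size is modest: about 1.45 ms per subject at N = 40 or 1.2 ms at N = 48, under the assumed +60 ms and 2 ms. At the planned effect, one such subject would not usually change the result (upper limit about 7.6 ms if kept). It could if the true effect were nearer the margin or if two subjects were stopped. The events should be rare. The reason to act is that this trial exists to detect them, and the rule should be settled before any occurs.

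**What to change.** Add to SAP 5.2: Holters not performed because a subject was discontinued (stopping rule, adverse event or withdrawal) are not major deviations, and that subject's completed periods stay in the Per Protocol Set. Word it so that it also covers the adjacent Major row on missing baseline triplicates, which could be read the same way for periods never started.

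This stays within the Per Protocol definition in Protocol 11.3.2, because it settles which events count as major and leaves the unit of exclusion alone. The clinical stopping rule is untouched. The cost is a sentence of SAP text and the matching programming. The Per Protocol Set will then contain some incomplete subjects, which the planned mixed model with a random subject effect accepts without imputation.
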